#### **8.5.7.2. Pregnancy**

The Investigator will collect pregnancy information on any female Participant who becomes pregnant while participating in this study. The initial information will be submitted to the Sponsor within 24 hours of learning of a Participant's pregnancy.

Further dosing will be discontinued for any female Participant who becomes pregnant during the study.

The Participant will be followed to determine the outcome of the pregnancy. The Investigator will collect follow-up information on the Participant and the neonate, and the information will be forwarded to the Sponsor. Generally, follow-up will not be required for longer than 6 to 8 weeks beyond the estimated delivery date.

While pregnancy itself is not considered to be an AE or SAE, any pregnancy complication or elective termination of a pregnancy for medical reasons will be reported as an AE or SAE. A spontaneous abortion (occurring at < 22 weeks gestational age) or stillbirth (occurring at > 22 weeks gestational age) is always considered to be an SAE and will be reported as such. Other abnormal pregnancy outcomes (e.g., fetal death, congenital anomalies, ectopic pregnancy)

are also considered SAEs and will be reported.

Any post-study pregnancy-related SAE considered possibly, probably, or definitely related to the study drug by the Investigator will be reported to the Sponsor. While the Investigator is not obligated to actively seek this information in former study Participants, he or she may learn of an SAE through voluntary reporting.

The Investigator will record a narrative description of the course of each pregnancy and its outcome.

#### **8.5.8. Disease-Related Events and/or Disease-Related Outcomes Not Qualifying as AEs or SAEs**

Except for signs and symptoms of diabetic peripheral neuropathy (i.e., numbness, pain, tingling or burning sensation, cramps, and increased sensitivity to touch), all disease-related events or disease-related outcomes qualify as AEs or SAEs.

#### **8.6. Immunogenicity Assessments**

Pre-dose and post-dose (after 2 hours  $\pm$  1 hour post last injection) blood samples will be collected on Days 0 and 14, post-dose on Day 90, and pre-dose and post-dose samples will be collected on Day 104 for measurement of levels of TNF- $\alpha$ , IL-1 $\beta$ , IFN- $\gamma$ , IL-6, IL-4, IL-10, and IL-12p70.

A blood sample will be collected pre-dose on Days 0 and 90, and on Days 60, 150, and 180 for detection of anti-HGF antibodies.

## 9. STATISTICAL CONSIDERATIONS

Detailed statistical methods are described in the Statistical Analysis Plan (SAP).

### 9.1. Sample Size Determination

The sample size for the primary efficacy endpoint is calculated based on the hypothesis for the primary efficacy endpoints.

The primary efficacy endpoint is the change in the mean ADPS recorded at the Day 0 and Day 180 Visits obtained from 5 to 7 daily entries in the BPI-DPN eDiary prior to those Visits.

The statistical hypothesis for the primary efficacy endpoint (Hypothesis I) is:

$$H_0: \mu_t = \mu_p \text{ versus } H_a: \mu_t \neq \mu_p, (I)$$

where  $\mu_t$  and  $\mu_p$  are the mean pain change from Baseline to 6-month follow-up for the Engensis and Placebo groups, respectively. A negative mean value means a reduction in the pain score, and a positive mean value means an increase in the pain score. The statistical power is 80%.

Details on the assumptions for sample size determination are described in the Statistical Analysis Plan.

### 9.2. Populations for Analyses

#### 9.2.1. Intent-To-Treat Population

This subset includes all Participants who are randomized (Participants). All Baseline characteristics will be summarized based on intent-to-treat (ITT). Participants in the ITT will be analyzed according to original treatment assignment, regardless of actual treatment received. The primary analyses of the primary and secondary efficacy endpoints will be based on this ITT population.

#### 9.2.2. Safety Population

The safety analysis population will contain all Participants who receive at least one Study Injection.

#### 9.2.3. Modified Intent-to-Treat Population

The modified ITT (mITT) population includes all Participants who meet the following:

- Underwent (any) injections
- Correctly completed at least 5 out of 7 days of the BPI-DPN eDiary at Baseline and the 6-month follow-up

Participants will be grouped based on the randomly assigned treatments, not the actual treatment received. The mITT population will be used in the sensitivity analyses for the primary and secondary efficacy endpoints.

#### 9.2.4. Per Protocol (PP) Population

The Per Protocol population is a subset of mITT. It includes all mITT Participants who meet all the following criteria:

- The Participant met major protocol eligibility criteria determined by Clinical Data Review Committee (CDRC) prior to database lock and breaking the randomization codes.
- The Participant received all injections based on the randomized treatments and had a Day 180 Visit, including a 7-day ADPS.

Additional criteria, if any, will be established before unblinding the randomization code by the independent CDRC that is masked to the treatment information of each Participant.

The PP population will be used in the sensitivity analyses for the primary and secondary efficacy endpoints.

### 9.3. Statistical Analyses

The Statistical Analysis Plan will be finalized prior to database lock and will include a more technical and detailed description of the statistical analyses described in this section. This section is a summary of the planned endpoints and the statistical analyses.

#### 9.3.1. Primary Endpoint(s)

As described in Section 3, the primary efficacy endpoint is:

Change in the means of the ADPSs from the BPI-DPN from the 7 days prior to the Day 0 Visit to the 7 days prior to the Day 180 Visit for Engensis compared to Placebo in the ITT population

#### 9.3.2. Secondary Endpoints

The secondary efficacy endpoints include the following:

- Change in the means of the Worst Pain Scores from the BPI-DPN from the 7 days prior to the Day 0 Visit to the 7 days prior to the Day 180 Visit for Engensis compared to Placebo
- Proportion of Responders ( $\geq 50\%$  reduction in the means of ADPSs from the BPI-DPN) from the 7 days prior to the Day 0 Visit to the 7 days prior to the Day 180 Visit for Engensis compared to Placebo

Safety endpoints include:

- Incidence of TEAEs and TESAEs for Engensis compared to Placebo
- Incidence of injection site reactions for Engensis compared to Placebo
- Incidence of clinically significant laboratory values for Engensis compared to Placebo
- Change from Baseline in the cytokine profile through post-dose on Day 104 for Engensis compared to Placebo
- Presence of anti-HGF antibodies following Engensis administration compared to Placebo

### 9.3.3. Exploratory Efficacy Endpoints

The exploratory efficacy endpoints include the following:

- Patient Global Impression of Change (PGIC) on Day 90 and on Day 180 for Engensis compared to Placebo
- Proportion of Responders (based on  $\geq 50\%$  reduction in the means of ADPS from the BPI-DPN) from the 7 days prior to Day 180 who were Responders on Day 104 (final injection visit) for Engensis compared to Placebo
- Changes in the Bedside Sensory Testing (BST) from Baseline to Day 90 and to Day 180 for Engensis compared to Placebo
- Proportion of Responders ( $\geq 20, 30, 40, 60$  and  $70\%$  reduction in the means of ADPSs from the BPI-DPN) from the 7 days prior to the Day 0 Visit to the 7 days prior to the Day 90 Visit and the 7 days prior to the Day 180 Visit for Engensis compared to Placebo
- Changes in the means of the Average Daily Pain Scores (ADPSs) from the BPI-DPN from the 7 days prior to the Day 0 Visit to the 7 days prior to the Day 90 Visit for Engensis compared to Placebo
- Changes in the severity scores (Worst Pain, Least Pain, Average Pain, and Pain Right Now) from the full BPI-DPN from the 7 days prior to the Day 0 Visit to the 7 days prior to the Day 90 Visit and the 7 days prior to the Day 180 Visit for Engensis compared to Placebo
- Changes in Michigan Neuropathy Screening Instrument (MNSI) assessments from Baseline to Day 90 and to Day 180 for Engensis compared to Placebo
- Changes in Quality of Life in the SF-36 from Baseline to Day 90 and Day 180 for Engensis compared to Placebo
- Changes in Quality of Life in the EQ-5D from Baseline to Day 90 and to Day 180 for Engensis compared to Placebo
- Changes in the means of the daily use of rescue medication from Day 0 to Day 90, from Day 0 to Day 180, and from Day 90 to Day 180 for Engensis compared to Placebo

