
 
To evaluate the possibility of cellular and/or humoral responses to Engensis compared to Placebo in Participants with painful DPN in the feet and lower legs
 
	
 
Change from Baseline in the cytokine profile through post-dose on Day 104 for Engensis compared to Placebo
 

Objectives	Endpoints
	
 
• Presence of anti-hepatocyte growth factor (HGF) antibodies following Engensis administration compared to Placebo
 

Exploratory Efficacy	

 
• To evaluate the efficacy of IM administration of Engensis on Quality of Life and Patient Reported Outcomes in Participants with painful DPN in the feet and lower legs as compared to Placebo
 
	
 
• Patient Global Impression of Change (PGIC) on Day 90 and on Day 180 for Engensis compared to Placebo
 

 
• To evaluate the durability of the analgesic response to IM administration of Engensis in Participants with painful DPN in the feet and lower legs as compared to Placebo
 
	
 
• Proportion of Responders (<math>\geq 50\%</math> reduction in the means of ADPSs) from the 7 days prior to the Day 180 Visit who were Responders on Day 104 (final injection visit) for Engensis compared to Placebo
 

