Objectives	Endpoints
	
 
• Presence of anti-hepatocyte growth factor (HGF) antibodies following Engensis administration compared to Placebo
 

Exploratory Efficacy	

 
• To evaluate the efficacy of IM administration of Engensis on Quality of Life and Patient Reported Outcomes in Participants with painful DPN in the feet and lower legs as compared to Placebo
 
	
 
• Patient Global Impression of Change (PGIC) on Day 90 and on Day 180 for Engensis compared to Placebo
 

 
• To evaluate the durability of the analgesic response to IM administration of Engensis in Participants with painful DPN in the feet and lower legs as compared to Placebo
 
	
 
• Proportion of Responders (<math>\geq 50\%</math> reduction in the means of ADPSs from the BPI-DPN) from the 7 days prior to the Day 180 Visit who were Responders on Day 104 (final injection visit) for Engensis compared to Placebo
 

 
• To determine whether IM administration of Engensis has a positive effect (reverses/reduces pain, improves neurological function and quality of life) on painful DPN as compared to Placebo
 
	
 
• Change in the Bedside Sensory Testing (BST) from Baseline to Day 90 and to Day 180 for Engensis compared to Placebo
 
• Proportion of Responders (<math>\geq 20, 30, 40, 60,</math> and <math>70\%</math> reduction in the means of ADPSs from the BPI-DPN) from the 7 days prior to the Day 0 Visit to the 7 days prior to the Day 90 Visit and the 7 days prior to the Day 180 Visit for Engensis compared to Placebo
 
• Change in the means of the ADPSs from the BPI-DPN from the 7 days prior to the Day 0 Visit to the 7 days prior to the Day 90 Visit for Engensis compared to Placebo
 
• Changes in the severity scores (Average Daily Pain, Worst Pain, Least Pain, and Pain Right Now) from the full BPI-DPN from the 7 days prior to the Day 0 Visit to the 7 days prior to the Day 90 Visit and the 7 days prior to the Day 180 Visit for Engensis compared to Placebo
 

Objectives	Endpoints

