**10.5.2. Definitions**

Active Infection	Chronic infection or severe active infection that may compromise the Participant's well-being or participation in the study, in the Investigator's judgment
Allowed Opioid Use	When Participants require opioids for non-DPN post-trauma pain or pain after surgery that was unanticipated during Screening, short-acting formulations are to be used, enabling a more rapid washout and reduced effect on DPN-related pain
Average Daily Pain Score (ADPS)	The mean of at least 5 daily pain scores recorded for Question 5 of the BPI-DPN (Section 10.7) in eDiary during the 7 days prior to the Visits on Day 0, Day 90, and Day 180
Worst Daily Pain Score	The mean of at least 5 worst daily pain scores recorded for Question 3 of the BPI-DPN (Section 10.7) in eDiary during the 7 days prior to the Visits on Day 0, Day 90, and Day 180
Day 14, etc.	Day 14 (for example) refers specifically to the actual day of the Visit designated as the Day 14 Visit, and not to the 14 th day of the study for a Participant.
Drug Abuse	The habitual taking of addictive or illegal drugs
Drugs of Abuse	Amphetamines, barbiturates, benzodiazepines, buprenorphine, cocaine, fentanyl, meperidine, methadone, opiates, oxycodone, oxymorphone, phencyclidine, tramadol
EMLA Cream	A mixture of lidocaine 2.5% and prilocaine 2.5%
First-degree relative	Parent, sibling, or child
Highly Effective Contraception Method	See Section 8.5.7
Injection Site Reaction	An AE located in close proximity to the injection sites on the calves and first observed within 48 hours following Study Injections
Investigator	The PI or appropriate Study Site personnel whom the PI designates to perform a certain duty
Lower Leg	The part of the leg between the knee joint and the ankle joint. Does not include the foot.
Medical Monitor	The Responsible Medical Officer or designee
Participant	An individual who has signed informed consent to be entered into the study
Placebo	Placebo comprises 45 mg sodium chloride and 55 mg sucrose in 5 mL of water for injection. Engensis vials contain the same excipients.
Primary HPV Test	A Primary HPV test is an HPV test that is done by itself for screening. The US Food and Drug Administration has approved certain tests to be primary HPV tests. This is the recommended test by the ACS; however, it is not always available.

Safety Analysis Population	All Participants who receive a Study Injection
Site	A clinical research facility participating in the VMDN-003-2 study

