•	To evaluate the durability of the analgesic response to IM administration of Engensis in Participants with painful DPN in the feet and lower legs as compared to Placebo	•	Proportion of Responders (≥ 50% reduction in the means of the ADPSs) from the 7 days prior to the Day 180 Visit who were Responders on Day 104 (final injection visit) for Engensis compared to Placebo
•	To determine whether IM administration of Engensis has a positive effect (reverses/reduces pain, improves neurological function and quality of life) on painful DPN as compared to Placebo	•	Change in the Bedside Sensory Testing (BST) from Baseline to Day 90 and to Day 180 for Engensis compared to Placebo Proportion of Responders (≥20, 30, 40, 60, and 70% reduction in the means of the ADPSs from the BPI-DPN) from the 7 days prior to the Day 0 Visit to the 7 days prior to the Day 90 Visit and the 7 days prior to the Day 180 Visit for Engensis compared to Placebo

Objectives	Endpoints
	• Change in the means of the ADPSs from the BPI-DPN from the 7 days prior to the Day 0 Visit to the 7 days prior to the Day 90 Visit for Engensis compared to Placebo
	 Changes in the severity scores (Average Pain, Worst Pain, Least Pain, and Pain Right Now) from the full BPI-DPN from the 7 days prior to the Day 0 Visit to the 7 days prior to the Day 90 Visit and the 7 days prior to the Day 180 Visit for Engensis compared to Placebo
	 Changes in Michigan Neuropathy Screening Instrument (MNSI) assessments from Baseline to Day 90 and to Day 180 for Engensis compared to Placebo
	• Change in the 36-Item Short Form Health Survey (SF-36) from Baseline to Day 90 and to Day 180 for Engensis compared to Placebo
	 Change in the EuroQol Health Utilities Index (EQ-5D) from Baseline to Day 90 and to Day 180 for Engensis compared to Placebo

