7.2. Visit Windows

Data at each scheduled follow-up visit will be analyzed according to the nominal visit identified on the data record.

In case of multiple different visits with the same nominal visit designation, the visit with the visit date closest to the target days of each protocol-specified visit schedule will be used for the efficacy analyses. For visits with the same distance to the target days, the later nominal visit record will be used. Data from all visits will be provided in the data listings.

If a subject fails to complete a study visit but provides necessary eDiary data during the time period expected for that visit (i.e. based on study day relative to the date of the first dose in VMDN-003-2), those eDiary data will be used to derive applicable endpoints. Day 90 endpoint would be derived by the eDiaries recorded 7 days up to 90 days from the date of first dose. Also, Day 104 endpoint would be derived by the eDiaries recorded 7 days up to 104 days from the date of first dose. Similarly, Day 180 endpoint would be derived by the eDiaries recorded 7 days up to 180 days from the date of first dose. Otherwise, if subject completes study visit, then date of visit will be used to derive applicable endpoints.

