7.4. Multiplicity Adjustment

To control the family-wise type 1 error rate at 0.05 for multiplicity across the primary and secondary

endpoints, a hierarchical testing strategy³ will be used. The hierarchical testing strategy starts with the primary endpoint followed by sequential testing of the secondary endpoints. The statistical significance will be evaluated in the following order: If a statistical significance at the 0.05 level (2-sided) is shown for the first ranking order, then the next endpoint in the immediate subsequent order will be evaluated; evaluation of subsequent endpoints will continue in the same manner. If no statistical significance is shown at 0.05 level at any endpoint, then the endpoint and all subsequent endpoints will not be considered statistically significant, regardless of their p-values.

The hierarchical testing order follows:

- 1. Change in the means of the Worst Pain Scores from the BPI-DPN from the 7 days prior to the Day 0 Visit to the 7 days prior to the Day 180 Visit for Engensis compared to Placebo
- Proportion of Responders (≥ 50% reduction in the means of ADPSs from the BPI-DPN)
 from the 7 days prior to the Day 0 Visit to the 7 days prior to the Day 180 Visit for
 Engensis compared to Placebo

The p-values for other secondary and exploratory endpoints will be used for informative or supportive purposes only. Therefore, there will be no further adjustment for multiple tests.

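### The exploratory durability endpoint, as worded, conditions on Day 180 response instead of Day 104 response, which tends to flatter a drug whose effect has worn off

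*Protocol*

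**What the plan says.** The endpoint appears four times, always conditioned in the same order. Protocol 9.3.3 has it as responders "from the 7 days prior to Day 180 who were Responders on Day 104 (final injection visit) for Engensis compared to Placebo". The Synopsis (Protocol 1.1) and Protocol Section 3 have "from the 7 days prior to the Day 180 Visit who were Responders on Day 104 (final injection visit) for Engensis compared to Placebo". SAP Section 2 ends the same way: "who were Responders on Day 104 (final injection visit) for Engensis compared to Placebo". A responder has at least a 50% reduction in mean ADPS.

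The paired objective in Protocol Section 3 is "To evaluate the durability of the analgesic response to IM administration of Engensis", and this is the only endpoint set against it in the objectives table.

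On the Day 104 value the two documents differ. The ADPS definition in Protocol 10.5.2 covers scores "during the 7 days prior to the Visits on Day 0, Day 90, and Day 180", with no Day 104. SAP 7.2 does supply a Day 104 window. For a missed visit, "Day 104 endpoint would be derived by the eDiaries recorded 7 days up to 104 days from the date of first dose"; for a completed visit, the visit date is the anchor.

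On inferential status, SAP 7.4 says: "The p-values for other secondary and exploratory endpoints will be used for informative or supportive purposes only".

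**The concern.** Durability means that people who had responded by the last injection visit are still responding later. That needs Day 104 responders in the denominator. The wording puts Day 180 responders there and asks how many were already responders on Day 104.

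The two proportions share a numerator (responders on both days) but behave differently. If a drug works at Day 104 and has worn off by Day 180, its pool of Day 180 responders is no larger than Placebo's, but more of those people will also have responded at Day 104. The literal proportion therefore rises because the early effect was lost. A drug whose effect appears only after Day 104 is penalised.

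Either conditional proportion also compares arms within a subset chosen by a post-randomisation outcome, so neither is a randomised comparison. At stake is any supportive statement about durability. That matters to the sponsor because Protocol Section 2 introduces the product as one for durable management.

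**Working it through.** **Planning inputs.** The documents give no figure for this endpoint, so I first checked the SAP Section 5 inputs that the illustration reuses: difference 1 point, SD 2.18, 1:1 allocation, two-sided 5%, power 80%. The normal formula n = 2(1.96 + 0.842)² × 2.18² / 1² gives 75 per arm, or 150. A two-sample t-test gives a total of 151.1, rounded up to 152, with power 0.802 at 76 per arm. This matches the SAP.

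**Model.** Pain changes at Day 104 and Day 180 are bivariate normal with SD σ = 2.18 and within-person correlation ρ. With baseline B, a responder has a change of -B/2 or lower. Then:

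- p104 = Φ((-B/2 - μ104)/σ) and p180 = Φ((-B/2 - μ180)/σ)
- J = probability of response on both days (bivariate normal)
- literal proportion = J / p180
- forward proportion = J / p104

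From the SAP: σ = 2.18, and mean change about -1.5 on Placebo and -2.5 on active drug (rounded from the VMDN-003b row of Table 3, -1.49 and -2.52). Assumed, because the documents give neither: B = 6 and ρ = 0.7, equal in both arms.

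With B = 6 the threshold is -3. Without drug effect, (-3 + 1.5)/2.18 = -0.688, so p = 0.246. With drug effect, (-3 + 2.5)/2.18 = -0.229, so p = 0.409.

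| Profile | Day 104 | Day 180 | Both days (J) | Literal J/p180 | Forward J/p104 |
|---|---|---|---|---|---|
| Placebo | 24.6% | 24.6% | 14.7% | 59.9% | 59.9% |
| Drug, worn off by Day 180 | 40.9% | 24.6% | 19.7% | 80.0% | 48.0% |
| Drug, fully sustained | 40.9% | 40.9% | 28.6% | 69.9% | 69.9% |
| Drug, effect only after Day 104 | 24.6% | 40.9% | 19.7% | 48.0% | 80.0% |

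(Ratios use unrounded values.) The literal proportion ranks the worn-off drug above the sustained one. The forward proportion places the worn-off drug below Placebo.

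**In counts, per arm of 76.** Placebo has 18.7 responders on each day and 11.2 on both. The worn-off drug has 31.1 at Day 104, 18.7 at Day 180 and 14.9 on both. It loses 31.1 - 14.9 = 16.2 of 31.1 (52%), while Placebo loses 18.7 - 11.2 = 7.5 of 18.7 (40%). The literal denominators are only about 19 per arm.

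**Range.** Over B = 5 to 8 and ρ = 0.3 to 0.9, worn-off drug minus Placebo is +16 to +23 points on the literal proportion and -3 to -23 points on the forward one. In a wider grid of 1,040 settings with equal correlation in both arms (B = 4 to 10, ρ = 0 to 0.95, Day 104 effect 0.3 to 1.5, no Day 180 effect), the literal proportion favoured the worn-off drug every time and the forward proportion never did.

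**Where the direction breaks.** With unequal correlation the literal result can reverse: ρ = 0.9 on Placebo and 0.6 on drug (B = 6) gives 77.0% on Placebo against 73.5% on drug. With 0.7 on drug, it still favours the drug, at 80.0%.

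**The case against.** Four points deserve weight.

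First, the denominator may be settled elsewhere. The SAP contents list a Section 8.4.6 on exploratory endpoints, but in the public text heading 8.4 runs straight into 8.5, and Section 4 passes from heading 4.1 into the middle of the exploratory list. The surviving bullets there carry calculation notes, and the durability bullet falls in the gap. This gap cannot be counted against the plan. It stands as a condition on the conclusion, though all four visible statements still need to agree with whatever that text says.

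Second, the sentence may be loosely phrased and meant as the forward proportion, in which case a worn-off drug is correctly shown as less durable. That is possible, but nothing visible says so.

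Third, the consequence is limited. No alpha is attached to the endpoint. If the effect had gone by Day 180, the primary endpoint and the 50% responder secondary, both at Day 180 in the ITT population, would have no true benefit to show beside a favourable durability figure. Protocol 8.3.1 also plans daily ratings to describe onset, peak and duration of relief. All of this stands.

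Fourth, response on both days among all randomised participants does not isolate durability either: a worn-off drug still scores 19.7% against 14.7% on Placebo. This is correct. But that rate puts the sustained drug highest (28.6%) and compares randomised groups, so it is useful if paired with the forward proportion.

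**Conclusion.** The point holds for the wording as it stands. The endpoint conditions in the reverse direction to its objective, and with similar within-person correlation in both arms it tends to make a worn-off drug look more durable than Placebo: about 80% against 60% at the central assumptions, an apparent advantage of 16 to 23 points over the range examined. The SD and mean changes come from the SAP; baseline and correlation are assumptions.

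A reader might infer that the endpoint must always mislead in this way. It need not: the direction depends on an early drug effect and on comparable correlations, and it can reverse. Nor do the documents support saying that the plan defines no other denominator, because the relevant SAP text is not visible, or that the trial's main conclusion is at risk, because the endpoint is exploratory. What is affected is the supportive durability statement.

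**What to change.** Unless the SAP sections not visible here already do so, change the following in the protocol (Synopsis, Section 3, Section 9.3.3) and the SAP (Section 2 and the matching analysis text):

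1. Define the durability proportion with Day 104 responders (at least 50% ADPS reduction from baseline) as the denominator and those still responding at Day 180 as the numerator. Report it descriptively by arm, because it conditions on a post-randomisation outcome.
2. Make the between-arm comparison the proportion of all randomised participants who respond at both Day 104 and Day 180. State whether missing data count as non-response or are imputed. Note that this rate is not by itself a pure durability measure and should be read with item 1.
3. Add Day 104 to the ADPS definition in Protocol 10.5.2 so that it matches SAP 7.2.

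The cost is wording and a small programming change. No new data are needed: the partial BPI-DPN, which includes the average-pain question, is completed daily between the full-questionnaire periods, and SAP 7.2 already derives a Day 104 value.
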